1.3 Primary objective

Estimate the difference in hospital admission rate at initial episode of care comparing ABSSSI patients receiving care before implementation of the new critical pathway and after implementation.

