2.0 Study Objectives

2.1 Primary Objective

The primary objective of the study is to estimate the difference in hospital admission rate at the initial episode of care comparing ABSSSI patients receiving care before implementation of the new critical pathway and after implementation.

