6.2 Statistical Methods

Descriptive analyses will be performed as follows: for continuous variables, patient counts, percentages, means, 95% confidence intervals (CI) of the means, standard deviations (SD), medians, first (25th percentile) and third (75th percentile) quartiles, minima and maxima, and number missing (where applicable) will be reported. For categorical variables, patient counts and percentages for each category, as well as number missing (where applicable), will be reported. Where applicable, summaries for continuous variables will include frequencies and percentages for discrete categories (e.g., number of ED visits: 0, 1, 2, and so forth).

For applicable categorical measures of baseline characteristics (including demographics, infection characteristics at baseline, comorbid conditions reported at baseline, and prior healthcare resource utilization within past 3 months), the pre-period cohort will be compared with the post-period cohort using chi-square tests or Fisher's exact tests, as appropriate. Differences in proportions of the pre-period and post-period and their corresponding asymptotic 95% confidence interval (CI) will be reported, where applicable. For applicable continuous variables, two-sided Student's t-tests and Mann-Whitney U tests will be used where normality assumptions have, and have not, been met, respectively. Where applicable, differences in descriptive statistics, proportions, and corresponding 95% CI will also be provided between the pre- and post-periods.

Hypothesis testing is specified for outcomes in section 6.2.5. All statistical testing, if done, will be two-sided at the significance level of 0.05 with the exception of the primary outcome, which will be tested with a one-sided Pearson chi-square test for proportion difference with a significance level of 0.05. Secondary outcomes will be analyzed predominantly by descriptive analyses and by number of incidences where applicable. Planned analyses are presented in Sections 6.2.5.2. All planned hypothesis testing and any

unplanned deviation from hypothesis testing for secondary outcomes will be purely exploratory, as adequate power will not likely be present to determine statistical significance. There will be no adjustments made for multiple comparisons.

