6.2.6 Outcomes

6.2.6.1 Primary Outcomes

Primary Outcome: Hospital Admission Rate at Initial Episode of Care

Hospital admission at initial episode of care will include infection-related stays upon discharge from the index ED visit (derived and described in Appendix B). Tables will reflect patient counts and percentages for hospital admission (yes, no) at the initial episode of care by the pre-period and post-period for the FAS population. Summary rows will be repeated by site.

The primary analysis will consist of hypothesis testing using a one-sided, two-sample Pearson chi-square test for proportion difference with a normal approximation. An appropriate alternative method will be selected if a major violation to an assumption is present.

Because the baseline characteristics of the pre-period may differ from those of the post-period, a secondary analysis using a multivariate logistic regression analyses will be implemented. This model will assume mutual independence between the sites.

Clinically relevant baseline characteristics of interest for the adjusted analysis include the following variables: age, gender (Male, Female), race (White/Caucasian, Black or African American, Other), employment status (Full-Time, Part-Time, None), insurance plan type (Private commercial plan, Government funded, Uninsured, Other), Charlson Comorbidity Index, lesion surface area (<75cm², =>75 cm² – 150 cm², >150 cm²), infection type (Wound infection, Cellulitis/erysipelas, Abscess), prior health resource use (Yes, No, Unknown), prior antibiotic treatment failure (Yes, No, Unknown), presence of SIRS criteria (<2 or >=2), presence of recurrent infection in prior 6 months (Yes, No, Unknown), any health resource use in prior 3 months (Yes, No, Unknown), as well as is patient was immunocompromised (Yes, No, Unknown). Patients will be defined as immunocompromised if they have evidence of any of the following at baseline: Connective tissue disease, diabetes mellitus, leukemia, or malignant lymphoma. Categorical variables will be collapsed where possible. The primary predictor variable will be a pre/post-period indicator, and potentially other selected characteristics will be forced into the model based on clinical rationale and distributions observed in the

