data (specifically imbalance between the pre- and post-periods). The stepwise selection of variables in the logistic regression will be done. The retention criteria in the model will be set as 0.1. The final model results will be presented in a table.

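### The primary objective is a difference in admission rate, but the plan specifies no covariate-adjusted difference: its only adjusted analysis is a logistic model with an unnamed effect measure

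*SAP*

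**What the plan says.** The objective is absolute in both documents. Protocol 1.3: "Estimate the difference in hospital admission rate at initial episode of care comparing ABSSSI patients", before versus after the pathway is introduced. SAP 2.1 agrees: "The primary objective of the study is to estimate the difference in hospital admission rate at the initial episode of care".

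SAP 6.2.6.1 plans two analyses of this outcome in the full analysis set (FAS):

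- **Primary, unadjusted.** A "one-sided, two-sample Pearson chi-square test for proportion difference with a normal approximation", with counts and percentages by period.
- **Secondary, adjusted.** The stated reason is "Because the baseline characteristics of the pre-period may differ from those of the post-period", and so "a secondary analysis using a multivariate logistic regression analyses will be implemented". The model has a pre/post indicator, a list of candidate baseline covariates and stepwise selection with a retention level of 0.1. On output, the section says only: "The final model results will be presented in a table".

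SAP 6.2 adds a general rule: "Where applicable, differences in descriptive statistics, proportions, and corresponding 95% CI will also be provided between the pre- and post-periods". It mentions no covariate adjustment. SAP 7.0 lists Table 10 (admission rate) and Table 11 (multivariate analysis of it). Their layouts are in a separate table-shell file.

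**The concern.** The two periods are independent, non-randomised groups of patients, so case mix is an obvious rival explanation for any change in admissions, and the SAP says as much. The adjusted model is there to address it. As written, the plan gives the target quantity without adjustment (a crude difference), or adjusts without saying on which scale the answer will appear. It does not specify the two together.

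If the adjusted result is reported in the usual way, as a conditional odds ratio for period, two problems follow:

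- It does not answer the objective in percentage points, and it has no direct counterpart in the crude rate difference.
- Anyone who derives a crude odds ratio from the tabulated percentages, to see whether adjustment changed anything, can be misled. Odds ratios are non-collapsible: adding prognostic covariates moves them even when those covariates are perfectly balanced.

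At stake is a covariate-adjusted answer to the trial's own primary question. The validity of the primary test is not in doubt.

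**Working it through.** **Inputs.** Admission rates of 38% (pre) and 23% (post), 161 patients per period and one-sided alpha 0.05 are from SAP 6.1.2 and Protocol 5.3. Attrition of 10% is the original assumption quoted in SAP 5.0. The spread of covariate risk is not given in the documents, so it is assumed and varied.

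**1. The plan's own figure.** Power = Φ{[0.15 - 1.645·√(2·0.305·0.695/n)] / √[(0.38·0.62 + 0.23·0.77)/n]}.
- n = 161: (0.15 - 0.0844)/0.0506 = 1.295, power 90.2%.
- n = 145 (161 less 10%): (0.15 - 0.0889)/0.0533 = 1.144, power 87.4%.

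The stated power of at least 80% is reproduced. It concerns the unadjusted difference, so nothing below changes it.

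**2. The design effect on three scales.**
- Difference: 0.23 - 0.38 = -0.15. SE = √[(0.2356 + 0.1771)/161] = 0.0506. 95% CI -0.15 ± 1.96·0.0506 = -24.9 to -5.1 points.
- Risk ratio: 0.23/0.38 = 0.605.
- Odds ratio: (0.23/0.77)/(0.38/0.62) = 0.487.

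**3. An odds ratio does not fix a difference.** Take a pre-period rate p, apply OR 0.487 to the odds p/(1 - p), and convert back:

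| Pre-period rate | Post-period rate | Difference (points) |
|---|---|---|
| 10% | 5.1% | -4.9 |
| 20% | 10.9% | -9.1 |
| 30% | 17.3% | -12.7 |
| 38% | 23.0% | -15.0 |
| 50% | 32.8% | -17.2 |

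**4. Non-collapsibility with perfect balance.** Let logit P(admission) = a + s·Z, with Z standard normal and identically distributed in both periods. Solve for a in each period so that the average risk is exactly 38% or 23%. The conditional OR is exp(a_post - a_pre).

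| Assumed SD s | a_pre | a_post | Conditional OR | Difference (points) |
|---|---|---|---|---|
| 0 (marginal) | - | - | 0.487 | -15 |
| 0.5 | -0.518 | -1.273 | 0.470 | -15 |
| 1.0 | -0.591 | -1.443 | 0.426 | -15 |
| 1.5 | -0.690 | -1.679 | 0.372 | -15 |

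A single balanced binary covariate (50% prevalence, assumed) shows the same pattern: the conditional OR is 0.479, 0.454, 0.412 or 0.378 for a covariate OR of 2, 4, 9 or 16.

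**5. The converse.** Suppose the adjusted OR equals the crude 0.487 and is read as showing no effect of case mix. With a standardised pre-period rate of 38%, the standardised post-period rate is 25.1% at s = 1.0 and 26.7% at s = 1.5. The adjusted differences are then -12.9 and -11.3 points, not -15.

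**6. The same model can return the target.** In 1,000 simulated trials (145 evaluable per period, balanced binary covariate with OR 4, both assumed), averaging the predicted risks with period set each way gave a mean difference of -0.151. The mean delta-method SE was 0.051 and the empirical SD 0.051. The covariate was fixed in advance, so this check does not cover stepwise selection.

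**The case against.** **What stands.**
- A reader might infer that the plan will report odds ratios and that an adjusted difference will never be estimated. The documents do not say so. SAP 6.2.6.1 speaks only of final model results, and the shell for Table 11 was not among the documents reviewed. The supportable statement is that no adjusted difference is specified in the visible text.
- The objective is met on its own scale without adjustment. Percentages are tabulated by period, and SAP 6.2 allows a difference in proportions with a 95% CI. Neither objective uses the word adjusted.
- Logistic regression is a standard secondary check for a binary outcome and is not wrong here.
- No crude odds ratio is planned. The misleading comparison of odds ratios would be the reader's own.
- The shift may be small. With 161 per period, SE(log OR) = √(1/61.18 + 1/99.82 + 1/37.03 + 1/123.97) = 0.248, so the crude OR has a 95% CI of 0.30 to 0.79. The shifts in step 4 are about 0.15, 0.54 and 1.09 of that SE, and the documents do not support any one SD over another.

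It is also tempting to say that the shift generally favours the pathway. That holds for a beneficial effect with no confounding. In a non-randomised comparison, confounding can move the adjusted odds ratio either way, and nothing in the documents supports a direction.

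**What does not stand.** The crude difference does not fill the gap, because SAP 6.2.6.1 introduces adjustment precisely because the periods may differ at baseline.

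**Conclusion.** The point holds as an omission in the specification. The objective is a rate difference between non-randomised periods, and no visible text specifies that difference after covariate adjustment. A conditional odds ratio would not supply it.

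At the design rates, with perfectly balanced covariates, the conditional OR could be 0.47, 0.43 or 0.37 against a marginal 0.49 while the difference stays at -15 points. These values rest on an assumed normal covariate score with SD 0.5, 1.0 or 1.5. They show that the problem can occur and are not a forecast for this trial.

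The primary test, power and sample size are untouched. This is a nearly free improvement to a secondary analysis, not an error in the primary one.

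**What to change.** Add to SAP 6.2.6.1, after the description of the logistic model:

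- Predict each FAS patient's probability of admission with period set to pre and then to post. Average each set of predictions over the FAS. Report the two standardised admission rates and their difference with a 95% CI.
- Take the CI from a covariate set fixed in advance, by the delta method or bootstrap. If stepwise selection at 0.1 is kept, use a bootstrap that repeats the selection in each resample. A delta-method interval from the selected model ignores the selection and would tend to be too narrow.
- Show the adjusted difference beside the crude difference and its CI in Tables 10 and 11, and base statements about robustness to case mix on these two differences. Any odds ratio can be shown as supporting detail.

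The cost is a few lines of SAP text, some programming and an update to two table shells. It uses the same data and type of model, with no new patients.

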2.4.1 Inclusion criteria

Eligible study subjects satisfy all of the following inclusion criteria^{1,10,11,24}

- Aged ≥ 18 years
- Present to the ED and meet clinical definition for ABSSSI¹⁰⁻¹¹
 - Present with the following infection types: cellulitis/erysipelas, wound infection, or major cutaneous abscess
 - Lesion size area requirements, as measured manually by the length multiplied by perpendicular width of wound (Appendix A).
 - Lesion size area ≥ 75 cm²
- Known or suspected infection caused by susceptible isolates of the following Gram-positive microorganisms: *Staphylococcus aureus* (including methicillin-susceptible and methicillin-resistant strains), *Streptococcus pyogenes*, *Streptococcus agalactiae*, *Streptococcus dysgalactiae*, *Streptococcus anginosus* group (including *S. anginosus*, *S. intermedius*, *S. constellatus*) and *Enterococcus faecalis* (vancomycin susceptible strains).
- Willing and able to return to the hospital or a designated clinic for scheduled visits, or be in contact with the study coordinator through telephone communication, as required by the protocol and the antibiotic treatment administered

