10.1 Measurement of lesion characteristics

Measurements are to be taken while the infected area is in a nondependent position, e.g., if infection was on the leg, the subject was lying down, not sitting or standing. All types of infections are to be measured as measurement of erythema upon enrollment and any subsequent physical follow-up visits. Maximal dimensions of erythema, both width and length, are to be recorded in centimeters. Investigators should attempt to find the infection edge that best distinguished erythema from non-erythematous skin. Erythema is to be measured in the dimension of maximal length. The maximal width is to be measured perpendicular to the axis of the maximal length. The maximal width measurement does not have to be in the center if the area of erythema is irregular. The length of the infection is to be multiplied by perpendicular width of wound.

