6.1 General Considerations

6.1.1 Analysis populations

Enrolled Set

The enrolled set consists of all patients who have signed informed consent and met all study eligibility criteria. Data will be summarized on disposition and baseline characteristics. Output will be summarized by study period (pre-period vs. post-period). All data listings will be reported for the enrolled set unless specified in Section 5.2.

Full Analysis Set

The full analysis set (FAS) population consists of all enrolled patients. Additionally, patients in the pre-period must receive at least one dose of antibiotics and patients in the post-period must receive at least one dose of dalbavancin for inclusion. All patients in the pre-period and post-period will be analysed. Data will be summarized by study period.

Data from all patients will be aggregated across sites, and all analyses related to protocol outcomes and baseline characteristics will be undertaken on the aggregate pre- and post-periods.

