6.2.4 Infection Characteristics at Baseline

Patient counts and percentages will be summarized by the pre-period and post-period for the FAS population for primary infection type, purulent drainage from primary lesion, primary lesion location, primary lesion size ($75\text{cm}^2 - 150\text{cm}^2$, $\geq 150\text{cm}^2$) number of additional lesion (e.g., 0, 1, 2, ≥ 3), fever, SIRS (met i.e., ≥ 2 criteria present, by individual criteria, and by number of criteria met) and recurrent/ABSSSI infection in prior 6 months. Descriptive statistics will be summarized for primary lesion size. Differences in infection characteristics between the pre- and post-period will be assessed using statistical significance testing. All of the aforementioned variables will be reflected in listings.

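### The secondary adjusted model enters lesion area as what is in effect one split at 150 cm²; log area, forced into the model, would adjust more fully at no cost.

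*SAP*

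**What the plan says.** Protocol 2.4.1 sets the entry threshold at "Lesion size area ≥ 75 cm²". Protocol 10.1 has maximal length and perpendicular width recorded in centimetres for all infection types, and then: "The length of the infection is to be multiplied by perpendicular width of wound". Area is therefore continuous at source.

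SAP 6.1.1 defines the enrolled set as "all patients who have signed informed consent and met all study eligibility criteria". It then states: "The full analysis set (FAS) population consists of all enrolled patients", with the further condition of at least one dose of antibiotic (pre-period) or dalbavancin (post-period). Under SAP 6.2.1, patients who fail eligibility appear only in listings.

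SAP 6.2.6.1 makes the primary analysis an unadjusted one-sided Pearson chi-square test on the full analysis set. Because the two periods may differ at baseline, it adds a multivariable logistic regression as a secondary analysis. One candidate covariate is "lesion surface area (<75cm², =>75 cm² – 150 cm², >150 cm²". In the same list, age and the Charlson index have no categories. Categories may be collapsed, some characteristics may be forced in on clinical grounds or observed imbalance (lesion area is not named), and the rest go through stepwise selection with retention at 0.1.

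SAP 6.2.4 tabulates lesion size as 75–150 and ≥150 cm², with no lower band, and adds: "Descriptive statistics will be summarized for primary lesion size".

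**The concern.** The three-level covariate does not match the population that the model is fitted to. With the lowest level empty, a 76 cm² lesion is treated like a 149 cm² one, and a 151 cm² lesion like an 800 cm² one.

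This matters because the comparison is not randomised. Using the same sites in both periods deals with differences between sites (Protocol 2.1.2), not with differences in patient severity. The enrolment process also differs. In the pre-period the treating physician is blinded to protocol content and to the enrolment decision (Protocol 2.3.1); in the post-period the treating physician may apply the checklist and enrol (Protocol 2.3.2). A shift in the severity of enrolled patients is possible, and the SAP itself counts lesion area among the clinically relevant characteristics. The logistic model is the only planned analysis of the primary outcome that could correct for such a shift.

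The cut-points also disagree between sections. A lesion of exactly 150 cm² (for example 15 × 10 cm) fits both bands in 6.2.4 and the lower band in 6.2.6.1.

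**Working it through.** **1. Can anyone occupy the <75 cm² level?** Entry requires area ≥75 cm² (Protocol 2.4.1). The enrolled set requires all criteria to be met, and the full analysis set is drawn from it (SAP 6.1.1). The level is empty by definition, which leaves 75–150 against >150 cm².

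**2. Does the empty level itself do damage?** The logistic model was fitted to simulated data once with the two-level factor and once with a three-level factor whose lowest level was empty. The period coefficient was −0.6437 in both. The empty level is numerically inert.

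**3. The plan's own figure, for scale.** SAP 6.1.2 claims at least 80% power with 161 per period, 38% against 23%, one-sided 0.05.
- n per period = [1.645·√(2·0.305·0.695) + 0.842·√(0.38·0.62 + 0.23·0.77)]² / 0.15² = 116.
- Power at 161 per period is 90.2%, and 87.2% at 144 (about 10% attrition). The claim reproduces, and lesion coding does not enter it.
- The planned effect as an odds ratio is (0.23/0.77)/(0.38/0.62) = 0.49.

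**4. How much confounding does one split remove? Closed form.** Assume that log area is roughly normal, that its effect on the log-odds of admission is linear, and that the shift between periods is small. A split with upper fraction q at cut-point c then removes the share φ(c)²/[q(1−q)].

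| Upper fraction q | Removed | Left |
|---|---|---|
| 0.5 | 0.637 | 36% |
| 0.3 | 0.576 | 42% |
| 0.2 | 0.490 | 51% |

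Example, with both inputs assumed: the periods differ by 0.3 SD in log area, and the admission odds ratio is 2 per SD. The confounding factor on the period odds ratio is exp(0.3·ln 2) = 1.23 with no lesion term. After the split it is exp(0.364·0.3·ln 2) = 1.08 for q = 0.5 and exp(0.51·0.3·ln 2) = 1.11 for q = 0.2.

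**5. A second check that respects the truncation at 75 cm².** Logistic models were fitted to 400,000 simulated patients per period with no true period effect. None of the following assumptions comes from the documents, except that 38% is the plan's own pre-period rate:
- lognormal area truncated at 75 cm², log-SD 0.6 or 0.9, underlying pre-period median 200 cm²;
- underlying post-period median 0.8, 0.67 or 0.5 times that;
- admission odds ratio per doubling of area 1.3, 1.6 or 2.0;
- pre-period admission 38%.

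This gives 2 × 3 × 3 = 18 scenarios.

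| Lesion term in model | Spurious period odds ratio (truth 1.00) |
|---|---|
| None | 0.64–0.95 |
| Split at 150 cm² | 0.84–0.97 |
| Pooled quartiles | 0.95–0.99 |
| Continuous log area | 1.00 |

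On the log-odds scale the split removes about 48–62% of the lesion-size bias and leaves 38–52%. The 1.00 in the last row is exact by construction, because the data were generated log-linearly.

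The two checks together give a remaining share of roughly 36–52%.

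**The case against.** The strongest reply is that little is at stake. The empty level is a drafting slip which the SAP's collapsing rule would clear up, and the fits in step 2 confirm that it changes nothing. The model is a secondary analysis, so no recoding can move the primary result. Both periods use the same entry criteria. The documents give no size imbalance and no effect of size on admission; the background in Protocol 1.1.3 discusses the need for parenteral therapy, haemodynamic instability, necrotizing fasciitis and unstable comorbidities as grounds for admission, not lesion size. A residual factor of 1.08 to 1.11 is modest beside a planned odds ratio of 0.49: a factor of 1.11 either way would move it to about 0.44 or 0.54. Correlated covariates such as infection type and SIRS might absorb some of the confounding.

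Most of this stands. A reader might infer that the empty level causes the loss of information, that confounding by lesion size is certainly left in, or that the trial's main result is biased by this coding. The documents support none of these readings. The loss comes from dichotomising, residual confounding is conditional, and the primary test adjusts for nothing, so it is the same under any coding.

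What does not stand is that the SAP's flexibility already solves the problem. Collapsing levels cannot restore size differences within a band. Forcing is optional and does not name lesion area. A continuous term alone would not be enough either, because stepwise selection could still drop it.

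**Conclusion.** The point holds for the secondary adjusted model only. Its lesion-area covariate is in effect one split at 150 cm², which adjusts less fully than the continuous measurement already collected.

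The consequence depends on two conditions that the documents neither state nor rule out: a difference in lesion size between periods within the bands, and an effect of size on admission. If both hold, roughly 36–52% of the lesion-size confounding can remain after the planned adjustment. That range rests on an assumed normal or truncated lognormal area with a log-linear effect. It illustrates what one split can leave behind and is not an estimate for this trial. A continuous term would do as well as shown only if its functional form is about right and area is measured with little error.

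The stated power and the primary chi-square result are untouched. The boundary mismatch at 150 cm² is real but concerns only lesions of exactly that size. This is a free improvement to the analysis, not an error that threatens the main conclusion.

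**What to change.** - In SAP 6.2.6.1, replace the three lesion-area categories with log(area in cm²), either linear or as a 3-knot restricted cubic spline, and state which before the outcome data are examined.
- In the same paragraph, name lesion area as forced into the model together with the period indicator, so that retention at 0.1 cannot remove it.
- In SAP 6.2.4, use non-overlapping descriptive bands of 75 to <150 and ≥150 cm².

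The cost is a few lines of SAP text. The linear form uses one model term and the spline two, no more than the two terms of the three-level factor as written (one of which is empty). Length and width are already recorded, so no new data are needed, and the sample size does not change.

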5.0 Changes in the Protocol Specified Analyses

Infection characteristics described in the protocol including hyperglycemia (>120mg/dL blood glucose or site-specific definition), thrombocytopenia (<150,000 platelet count or site-specific definition), acidosis (<7.35 pH of the blood or site-specific definition or described in medical chart), hyponatremia (<135 mEq/L blood sodium or site-specific definition), uremia (as described in medical chart), and anemia (14-18 g/dL hemoglobin for men or 12-16 g/dL hemoglobin for women or site-specific definition) will not be derived from laboratory values or reported in analysis.

An interim analysis was performed after the enrollment of approximately 75 patients to evaluate the original sample size. It was determined a sample size greater than 322 would be needed for hypothesis testing of the primary outcome of total number of days spent in the hospital. Factors that contributed to the large sample size include:

- The observed variation was larger than the original estimate (SD = 3.0 days).
- The observed attrition rate was larger than the original assumption (10%).

Additionally, the observed mean total LOS was much smaller than the protocol assumption (4.0 days). It was determined that observing a statistically significant reduction in the total number of days spent in the hospital in the post-period was unlikely.

Based on results of the interim analysis, an adjustment was made at the time of the analysis to revise the primary outcome from total admitted hospital days to hospital admission rate at initial episode of care. The initially estimated final enrollment of 322 subjects, including adjustments for attrition, would support one-sided hypothesis testing (two-sample Pearson chi-square test for proportion difference with equal group weights using a normal approximation) with a significance level of 0.05 and at least 80% power assuming hospital admission rate comparing the pre- and post-periods were 38% versus 23%. This change has been reflected in the protocol, Amendment Version 3.0.

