6.1.2 Sample size

Hospital admission rate, which is correlated to total hospital time for the study population, was largely unknown for purposes of sample size estimation. The final enrollment to support hypothesis testing for a primary outcome of total admitted hospital days was initially calculated as 322 subjects (161 subjects in each period). The sample size was evaluated after a planned interim analysis of pre-period data once 75 subjects were enrolled in the pre-period. Based on results of the interim analysis, an adjustment was made at the time of the analysis to revise the primary outcome from total admitted hospital days to hospital admission rate at initial episode of care. The initially estimated final enrollment of 322 subjects, including adjustments for attrition, would support one-sided hypothesis testing (two-sample Pearson chi-square test for proportion difference with equal group weights using a normal approximation) with a significance level of 0.05 and at least 80% power assuming hospital admission rate comparing the pre- and post-periods were 38% versus 23%.

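### Stepwise selection at 0.1 with an optional, undefined forcing step leaves the secondary adjusted analysis of admission open to residual confounding and to choices made after seeing the data

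*SAP*

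**What the plan says.** The primary outcome is "tested with a one-sided Pearson chi-square test for proportion difference with a significance level of 0.05" (SAP 6.2); no covariate enters that test. Because patients in the two periods may differ at baseline, SAP 6.2.6.1 adds that "a secondary analysis using a multivariate logistic regression analyses will be implemented". It names 14 covariates of clinical interest and makes period the main predictor.

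The choice of covariates is then left to three devices:

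- Some characteristics may potentially be "forced into the model based on clinical rationale and distributions observed in the" data, specifically imbalance between the periods.
- "The stepwise selection of variables in the logistic regression will be done".
- "The retention criteria in the model will be set as 0.1".

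The SAP gives no entry criterion, no definition of imbalance and no rule for collapsing categories. It plans neither a full-model sensitivity analysis nor an interval that allows for selection. Site is not among the 14 covariates, although the protocol's Data analysis section says that period differences will be assessed with account taken of site.

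**The concern.** The adjusted model is where a reader will look to see whether a fall in admissions reflects the pathway or a different mix of patients. Such a difference is plausible. In the pre-period, coordinators or core-team physicians decide enrolment and the treating physician is blinded to it (Protocol 2.3.1). In the post-period the treating physician may apply the checklist and enrol (Protocol 2.3.2). The post-period full analysis set also requires receipt of dalbavancin (SAP 6.1.1). The adjusted result has its own table under the primary-outcome label (Table 11 in SAP 7.0).

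A p-value rule keeps covariates that predict admission strongly in this sample. A confounder that is individually weak but shifted between periods can fail the rule, and several such losses add up. The final model's standard error is then computed as if that model had been chosen in advance. Forcing imbalanced covariates would repair much of this, but the SAP makes it optional and undefined, so two analysts could follow the same text and reach different adjusted results.

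**Working it through.** **1. The plan's own figure.** Inputs from SAP 6.1.2 and 6.2: 38% v 23%, 161 per period, one-sided α = 0.05.

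Power = Φ{[Δ − z·√(2p̄(1−p̄)/n)] / √([p₁(1−p₁)+p₂(1−p₂)]/n)}, with Δ = 0.15, p̄ = 0.305, z = 1.645.

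- n = 161: (0.15 − 1.645 × 0.0513)/0.0506 = 1.30, power 0.902.
- n = 145 (10% attrition): power 0.874.

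The stated power of at least 80% is reproduced. It belongs to the unadjusted test, not to the adjusted model.

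**2. Events and parameters.** Expected admissions are 161 × 0.38 + 161 × 0.23 = 61.2 + 37.0 = 98.2. The listed covariates, in order, take 1+1+2+2+3+1+2+2+2+2+1+2+2+2 = 25 parameters.

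- With period: 26 parameters, 98.2/26 = 3.8 events each.
- With about 8 sites (7 more terms): 33 parameters, 98.2/33 = 3.0.
- After removing the second health-resource-use term (2) and the lesion level below 75 cm² (1): 30 parameters, 98.2/30 = 3.3.

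**3. Effect of selection when there is no period effect.** Assumptions, none from the documents: 161 per period; 14 continuous covariates with pairwise correlation 0.2; six true confounders all shifted in the direction that favours the post-period; entry and retention at 0.1; period always in the model; imbalance taken as p < 0.05; 1,500 runs per row. Cells give bias in the period log-odds, one-sided 5% error, and mean model SE divided by empirical SD.

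| Shift (SD), log-odds per SD | Stepwise, period only forced | Stepwise, imbalanced covariates forced | Fixed model, all 14 |
|---|---|---|---|
| 0, 0.25 | +0.014, 5.1%, 0.955 | +0.014, 5.1%, 0.960 | +0.015, 5.1%, 0.961 |
| 0.20, 0.15 | −0.032, 7.2%, 0.933 | +0.001, 5.3%, 0.956 | +0.015, 4.6%, 0.964 |
| 0.25, 0.20 | −0.039, 8.6%, 0.929 | +0.007, 6.0%, 0.955 | +0.018, 5.1%, 0.969 |
| 0.35, 0.20 | −0.061, 10.4%, 0.901 | +0.012, 5.7%, 0.944 | +0.018, 5.5%, 0.960 |

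The Monte Carlo standard error near 5% is √(0.05 × 0.95/1500) = 0.6 points. In the last three rows the unadjusted comparison has bias −0.160, −0.263 and −0.373, so stepwise alone leaves 0.032/0.160 = 20%, 0.039/0.263 = 15% and 0.061/0.373 = 16% of it. Tested two-sided, stepwise alone gives 6.6%, 8.0% and 8.2%, against 5.9%, 6.6% and 5.1% for the fixed model.

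**4. With site in the data.** Assumptions: 18 covariate columns, six confounders shifted 0.25 SD, eight sites with SD 0.4, about 100 events, 1,500 runs. Errors at log-odds 0.2 and 0.3:

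- stepwise, period only forced: 11.5% and 9.9% (95% interval coverage 91.9% and 90.7%);
- stepwise with forcing: 6.4% and 7.0%;
- fixed model with site: 5.8% and 6.3% (coverage 93.9% and 94.0%).

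A further adverse scenario gives 12.4%, 7.4% and 6.4% in the same order. Across steps 3 and 4 the ranges under a common shift are 7.2% to 12.4% without forcing and 5.3% to 7.4% with it.

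**5. Behaviour at the planned effect.** The log odds ratio is ln[(0.23/0.77)/(0.38/0.62)] = −0.72. With site terms included:

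- ordinary fixed model: bias −0.089, coverage 92.8%;
- stepwise with forcing: bias −0.045, coverage 93.0%;
- fixed model with Firth penalisation: bias about −0.01, coverage 95% to 96%, with a one-sided error of about 5% under the null.

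**The case against.** The strongest reply is that stepwise selection without forcing is not the whole of the SAP's procedure. Forcing imbalanced covariates protects exactly the confounders that the simulations shift. In one run with 25 covariate columns it brought the error from 9.8% to 5.4%, against 5.1% for the full model. This stands: forcing reduces residual confounding and does not cause it. Its fault is that it is optional and has no threshold, so the SAP permits either result.

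The direction of the error is also assumed. With the same six confounders shifted in mixed directions, stepwise alone has bias 0.003 and error 6.8%, and 4.9% with forcing. This stands too. The documents report neither imbalances nor covariate effects.

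Third, an ordinary full model is no simple cure. At the planned effect it overstates the period effect more than stepwise with forcing does (step 5). That is correct for maximum likelihood with about three events per parameter, and it is why the fix needs penalisation. It does not defend selection.

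Finally, a reader might infer that this model is the trial's only control of confounding. The documents do not support that. Each site serves both periods, and admission rates for other infections are collected to account for temporal trends (Protocol 2.1.2) and compared by a Z-test (SAP 6.2.2). Those are controls by design or at site level; neither adjusts the outcome for patient characteristics.

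**Conclusion.** The point holds in a limited form. The only patient-level covariate adjustment of the primary outcome rests on selection at 0.1 and an undefined forcing step. If confounders shift together between periods, the one-sided 5% error of the adjusted test is about 7% to 12% with period alone forced, and about 5% to 7% if imbalanced covariates are forced. Which of these applies is decided after the data are seen. With no shift the error is near nominal (5.1%). The standard error is modestly too small: in step 3, about 7% to 10% for stepwise alone when confounding is present, 4% to 6% with forcing, and 3% to 4% even for the fixed model.

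These sizes rest on assumed confounding. They also rest on reading the adjusted test as one-sided, which the SAP states only for the chi-square test.

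A reader might go further and conclude that the primary p-value is compromised by the selection. It is not, because that test contains no covariates. Under the same assumptions its own unadjusted error is much larger (16% to 47% in step 3), but that is a separate weakness.

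**What to change.** In SAP 6.2.6.1, replace the stepwise and imbalance-forcing sentences with one model fixed before the data are analysed:

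- Terms: period, site, and the covariates already listed. Remove the second, near-identical health-resource-use term, and the lesion level below 75 cm², which eligibility should leave empty. Merge sparse levels, including Unknown, by a rule stated in advance.
- Estimation: Firth-penalised logistic regression.
- Reporting: the standardised risk difference between periods with its 95% interval, stating how the interval is obtained. Correct the intercept so that the mean fitted probability equals the observed admission rate, because Firth estimates pull fitted probabilities towards one half.

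If the sponsor prefers to keep selection, the SAP should state the entry criterion and a numerical forcing rule in advance, and bootstrap the whole procedure, selection included, to obtain the interval.

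The cost is SAP wording, slightly more analysis work and a slightly wider interval. No new data are needed.
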